1.3. Protocol Code: A-TRI-WEEK

EudraCT number: 2012-004970-24

1.9. Clinical Trial Phase: Phase IV

1.10. Objectives:**1.10.1. Main objective:**

The primary objective of this study is to determine the feasibility of maintaining virologic suppression on standard plasma viral load (limit of detection 37 copies/mL) of a once-daily dose reduction strategy of ATRIPLA® to three tablets per week in HIV-1-infected patients with sustained standard plasma viral load suppression for more than 2 years.

1.10.2. Secondary objectives:

- Virological study including: ultrasensitive viral load in plasma (limit of detection 1 copy/mL), and HIV-1 reservoir in peripheral blood mononuclear cells,
- Immunological study including: production of TREC, immune profile of activation (CD38 and HLA-DR) and senescence (CD57 and CD28) in CD4 and CD8 lineages, apoptosis (annexin V staining), and ratios of naïve T cells and effectors and memory cells (CCR7 and CD45RA).
- Pharmacokinetic study, including baseline plasma levels of efavirenz at the beginning and end of the study.
- Safety study, which includes: test on sleep quality, vitamin D levels, estimated glomerular filtration rate and plasma lipids at the beginning and end of the study, as well as general tolerability.

1.11. Design:

Open-label, randomized, Phase IV, prospective, pilot, single-center study.

1.12. Disease under study:

HIV infection (acquired immunodeficiency virus)

1.13. Assessment variables:**1.13.1. Main**

The primary endpoint of the study will be the proportion of patients who continue to have a viral load <37 copies/mL at 24 weeks using an intention-to-treat analysis.

1.13.2. Secondary

- Percentage of patients with virologic response viral load <1 copy/mL after 24 weeks.
- Change from baseline to 24 weeks in the viral reservoir of peripheral blood mononuclear cells
- Changes from baseline to 24 weeks in REBT production
- Changes in the immune profile of activation (CD38 and HLA-DR) and senescence (CD57 and CD28) in the CD4 and CD8 lineages, and in the proportions of naïve and effector and memory T cells (CCR7 and CD45RA).

- Changes in apoptosis levels in vitro by annexin V staining.
- Changes in plasma levels of efavirenz.
- Changes in sleep quality (Pittsburgh Sleep Quality Index), plasma levels of vitamin 25OH-D and lipids, and estimated glomerular filtration rate (CPK-EPI).
- Overall safety (reporting side effects, serious side effects, and discontinuation of treatment due to side effects)

1.14. Study population and total number of patients:

Adult patients with well-controlled chronic HIV infection and on treatment with ATRIPLA.® A total of 60 patients will be included.

1.15. Duration of treatment:

The approximate expected duration for the inclusion of patients is 12 months, and the duration of treatment and follow-up of the included patients will be extended by a maximum of 24 weeks.

1.16. Schedule and expected completion date:

The study is expected to begin, once the permits have been obtained, in March 2013. The recruitment period will be 48 weeks. The follow-up of the patients will last 24 weeks to start the study. The study is expected to be completed in October 2014.

3.1 Trial identification

Title:

Virologic and immunological safety of a dose reduction strategy with the

efavirenz/tenofovir/emtricitabine antiretroviral regimen

Open-label study, Phase IV, randomized, prospective, pilot, single-center.

1.3. Protocol Code: A-TRI-WEEK

Version / Date: 1.0, dated October 30, 2012. EudraCT

number: 2012-004970-24

3.7 Information on the laboratories or technical departments involved

Clinical evaluation of patients included in the study, routine blood/urine laboratory determinations and viral (HIV) determinations, will be performed at the Infections Day Hospital. And Retrovirology and Immunopathology Laboratory of the Infection Service:

The combination of efavirenz/tenofovir/emtricitabine has been the most frequently used contemporary treatment in clinical trials in people with no prior experience of antiretroviral treatment, and no other treatment regimen has shown superiority in efficacy against it (3). This combination is available as a fixed-dose combination in a single pill (ATRIPLA),® which represents the simplest antiretroviral regimen in Spain today. In the short term, there may be tolerability problems, neuropsychological side effects that are usually of little intensity and that in many cases resolve after the first four weeks of treatment (4). In addition, a small proportion of patients with well-identified risk factors such as older age, low CD4, low weight weight, nephrotoxic drugs, and underlying kidney disease may experience a progressive risk of tenofovir-associated renal dysfunction (5) that usually improves with discontinuation of tenofovir. There is evidence to suggest an association between increased bioavailability of efavirenz or tenofovir and the risk of developing side effects due to these drugs. For most patients on chronically stable treatment with ATRIPLA®, serious long-term side effects are not expected. ATRIPLA® has shown a better cost-effectiveness balance than other antiretroviral regimens (6). For all these reasons, ATRIPLA® has become one of the most popular antiretroviral regimens. At the end of 2011, approximately 25% of active patients (n=4400) treated at the Hospital Clínic de Barcelona were treated with ATRIPLA,® making this regimen the most frequently prescribed antiretroviral treatment. Currently, more than 1000 patients are receiving virologically effective treatment with ATRIPLA® at the Hospital Clínic de Barcelona, of which 75% have been on this treatment for more than two years.

Since antiretroviral treatment has to be taken indefinitely, the search for strategies to simplify it has been an important element in the development of antiretroviral regimens. The simplification of antiretroviral treatment in patients with sustained virologic suppression represents a strategy accepted by most therapeutic recommendations (7). The longer the viral suppression lasts, the greater the probability of maintaining sustained virological success (8-11). In patients with sustained virologic suppression, the absolute risk of virologic failure is low, and regimens with non-nucleoside reverse transcriptase inhibitors have consistently shown better virologic outcomes than regimens with protease inhibitors. Strategies to simplify antiretroviral treatment have aimed to minimize the risk of toxicity, seek greater convenience, and more recently reduce the cost of antiretroviral.

Although ATRIPLA® is the simplest antiretroviral regimen at present, there is potential for further simplification. Each of the individual components of ATRIPLA® has the longest half-lives of all currently available antiretrovirals: 40-55 hours for plasma efavirenz (12), 39 hours for intracellular emtricitabine triphosphate, and 150 hours for intracellular tenofovir diphosphate (13). In a discontinuation study, efavirenz plasma levels were estimated to exceed the adjusted IC95 for protein concentration (46.7 ng/mL) for a median of 6.7 days (IQR 4.7-9.2) after the last dose of efavirenz (14). Clinical information is available on the dosing of efavirenz at dose intervals greater than once daily (PHOTO study). The FOTO study was a 48-week observational study in which 30 patients with virologic suppression (<50 copies/mL) for at least three months prior to the study switched their usual antiretroviral treatment from a daily dose to a weekly schedule of 5 consecutive days on treatment (usually Monday through Friday) followed by 2 days without treatment (usually on the weekend) (15). Overall, virologic suppression was maintained in 90% of patients. More interestingly, however, ten of the 30 patients included were taking efavirenz along with tenofovir and nucleoside reverse transcriptase inhibitors with long half-lives such as didanosine or lamivudine, and none of these showed virologic failure. Following these promising results, researchers in the FOTO pilot study designed a 24-week open-label randomized study in which treatment with ATRIPLA® for five days a week would be compared to the standard dose of ATRIPLA® once a day (NCT00414635). So far, we have no information that results of this study have been reported.

In our daily practice, we have detected at least two patients on chronic treatment with ATRIPLA® who, for personal reasons, different in each case, decided to take the dose every other day instead of the standard daily dosage for more than 6 and 12 months respectively, without the plasma viral load having become detectable in any of them. On the other hand, a small preliminary survey of a randomly selected sample of 36 consecutive patients treated with ATRIPLA® for more than 2 years, who claimed to have no tolerability problems and with a persistently undetectable viral load during that period of time, showed that 78% saw a dose reduction to three days per week as more favorable than the standard daily dose. 14% did not care, and only 8% did not want to change their dosage, their main reasons being the fact that they were already fine as they were and the fear that they could lose the undetectability of the plasma viral load.

We intend to evaluate the possibility of effective simplification by moving from the standard daily dose of ATRIPLA® to a three-day-weekly dose in patients with sustained virologic suppression. Although antiretroviral treatment regimens have not so far contemplated dosing with intervals greater than once a day, the dosing of three times a week in the same way as that proposed in this project has been used with a high degree of compliance in the prophylaxis of *P. jirovecii* pneumonia in HIV-infected patients (16, 17).

Reducing the dosage of the most widely used antiretroviral treatment regimen as proposed in this project would reduce expenditure by 57%. In the case of the Hospital Clínic alone, this reduction in expenditure would mean going from 7.4 to 4.2 million euros per year. Since ATRIPLA® represents one of the most widely used regimens, the dose reduction strategy

could have a considerable impact on the budget for antiretroviral treatment within the policy of containing health expenditure promoted by the Spanish health authorities and more necessary today than ever in the current context of economic crisis (18). In addition, it can help reduce your already low risk of chronic toxicity. Finally, dose reduction is considered a popular measure and positively evaluated by a high proportion of treated patients. If our project obtains favorable results that support the dosage reduced to three days per week, the experimental regimen would become the simplest and cheapest among all the currently available regimens, including monotherapy with protease inhibitors.

Determination of plasma viral load and CD4 and CD8 cell counts have been key tools for clinical research and healthcare of HIV-positive patients until now. However, in patients with persistently undetectable viral load and relatively high CD4 counts, the simple determination of viral load and cell populations is unlikely to allow a fine distinction between the possible virological and immunological consequences of the dose reduction strategy to be evaluated. Therefore, viral reservoir analysis by determining proviral DNA and especially the proportion of that reservoir that produces viral particles can provide more detailed information on the virological safety of the new strategy (19). Similarly, the determination of plasma viral load using the most sensitive technique ("single copy assay" (limit of detection 1 copy/mL) (20) can discriminate whether this dose-reduction strategy produces any impact on viral replication that cannot be detected by the standard technique used in routine clinical practice. On the other hand, the extensive immunological study that is intended to be carried out (population analysis of the T lineage that includes its activation status and thymic production, among others) will allow us to exhaustively monitor the effects of any changes that may occur at this level on the study population (21-23). Therefore, we consider that the efficacy and safety of the dose reduction strategy of the efavirenz/tenofovir/emtricitabine regimen should be evaluated as consistently as possible with the previously mentioned virological and immunological tests.

Our study aims to conceptually confirm whether dose reduction of ATRIPLA® is feasible as a strategy and whether it entails any virological or immunological risk. If the results of this study are positive, they could form the basis for a randomized clinical trial of sufficient size to attempt to validate this strategy for future clinical use.

4.1 Investigational Drug Identification

Generic name: efavirenz, emtricitabine, and tenofovir disoproxil (as fumarate). 600 mg/200 mg/245 mg

Trade name: Atripla ®

Composition: Each tablet contains 600 mg efavirenz, 200 mg emtricitabine and 245 mg tenofovir disoproxil (as fumarate).

Pharmaceutical form: film-coated tablet.

4.2 Investigational Drug Information

The drug has been definitively approved by the Ministry of Health.

4.3 Treatment Regimen

Adults: The recommended dose of Atripla is one tablet, taken orally, once daily.

Description:

Atripla is a fixed-dose combination of efavirenz, emtricitabine, and tenofovir disoproxil fumarate. It is indicated for the treatment of human immunodeficiency virus-1 (HIV-1) infection in adults 18 years of age or older with virologic suppression at HIV-1 RNA levels of < 50 copies/mL on their current combination antiretroviral therapy for more than three months.

Route of administration: oral

Storage: Keep in the original packaging to protect it from moisture. Keep the bottle tightly closed.

Dosage Schedule:

Atripla ® is given 1 tablet 1 time a day.

Study period and treatment:

Randomization to two treatment groups: A or B

GROUP A (control): ATRIPLA® at standard daily dose (1 tablet daily) for a period of 24 weeks

GROUP B (experimental): ATRIPLA® at a dose three days per week (1 tablet Monday, Wednesday, and Friday) for a period of 24 weeks

4.4 Compliance Statement

The study will be carried out in accordance with the principles emanating from the Declaration of Helsinki, and according to the legal regulations in force (Royal Decree 223/2004), and will not begin until the approval of the reference CEIC and the approval of the AEMPS have been obtained.

Patients will be informed orally and in writing and all relevant information tailored to their level of understanding will be communicated to participants.

(See Attachment III: Patient Information Sheet and Attachment III: Written Consent Sheet.)

The patient will be informed that their participation in the study will be treated with the same confidentiality as their clinical documentation and that only the people involved in the study will have access to their data. The patient's name will not appear in any publication or communication of the results of the study.

4.5 Population under study

Adults with HIV-1 infection controlled on an outpatient basis in the Infectious Diseases Service of the Hospital Clinic of Barcelona.

- Immunological study including: production of TREC, immune profile of activation (CD38 and HLA-DR) and senescence (CD57 and CD28) in CD4 and CD8 lineages, apoptosis (annexin V staining), and ratios of naïve T cells and effectors and memory cells (CCR7 and CD45RA).
- Pharmacokinetic study, including baseline plasma levels of efavirenz at the beginning and end of the study.
- Safety study, including: sleep quality test (Pittsburgh Sleep Quality Index), vitamin 25OH-D levels, estimated glomerular filtration rate (CPK-EPI) and plasma lipids (triglycerides, total cholesterol and HDL) at the beginning and end of the study, as well as general tolerability.

6. Trial Design

Open-label study, Phase IV, pilot, prospective single-center.

6.1 Primary and Secondary Endpoints**Primary Endpoint:**

The primary endpoint of the study will be the proportion of patients who continue to have a standard plasma viral load (<37 copies/mL) at 24 weeks by intention-to-treat analysis.

Secondary endpoints:

- 1) The proportion of patients with ultrasensitive viral load (<1 copy/mL) after 24 weeks.
- 2) The change from baseline to 24 weeks in the viral reservoir of peripheral blood mononuclear cells
- 3) Changes from baseline to 24 weeks in TREC production, immune profile of activation (CD38 and HLA-DR) and senescence (CD57 and CD28) in CD4 and CD8 lineages, in naïve and effector and memory T cell ratios (CCR7 and CD45RA), and changes in apoptosis levels in vitro by annexin V staining.
- 4) Changes in plasma levels of efavirenz.
- 5) Changes in sleep quality (Pittsburgh Sleep Quality Index), plasma levels of vitamin D and lipids, and estimated glomerular filtration rate.
- 6) Overall safety (reporting side effects, serious side effects, and discontinuation of treatment due to side effects)

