6.6 Termination and/or discontinuation criteria

The treatment will be **compulsorily** terminated during the study for any of the following reasons:

- Virologic failure, defined by two consecutive determinations of standard viral load >37 copies/mL separated by one week from each other.
- I express the patient's wish.
- Medical decision.
- Death.
- Pregnancy detection during the study.

Treatment **may** be terminated during the study for any of the following reasons:

- The medical investigator determines that a SAE is possibly or likely related to the study drug.
- Failure to administer, evaluate, or other study requirements.

If the confirmatory result is ≥ 37 copies/mL, a genotypic resistance detection study would be scheduled and the most appropriate attitude towards modifying their antiretroviral treatment would be discussed with the patient. In this case, unless he or she is against it, the patient would continue in the study.

All other virologic studies and immunological studies should be determined exclusively at baseline and 24 weeks (except if there is earlier virologic failure, in which case it would be performed at the time of confirmation of failure rather than at 24 weeks), and their determination should be deferred at the end of the study. To this end, plasma and peripheral blood mononuclear cell samples should be stored appropriately at -80°C until the planned determinations are made.

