By ultracentrifugation (170000g, 30 minutes, 4°C) the HIV-1 virions present in 7mL of plasma will be concentrated, a volume to which will have been added a known concentration of an RNA transcript used as a non-competitive internal control for the monitoring of ultracentrifugation, extraction and amplification processes. The supernatant will be removed leaving a residual volume of 200 L, from which the viral RNA will be extracted using the commercial QIAamp MinElute Virus Spin (QIAGEN) kit, following the manufacturer's recommendations. The RNA obtained will be aliquoted and frozen at -80°C until use. The ultrasensitive quantification of the HIV-1 viral load will be performed by means of a one-step RT-PCR duplex in real time, using the STRATAGENE Mx3005P platform. For the amplification and detection of a conserved region of the HIV-1 gag gene, the primers and probes previously described by Palmer et al (2003) will be used. To detect the non-competitive internal control added to the sample, a set of specific primers and probe described above will be used (Almansa et al [PMID 21880131], Anton et al [PMID 20955912]). To carry out the quantification of the HIV-1 viral load and the internal control, two standard lines of serial dilutions from a known concentration of a standard will be amplified in parallel, one for the determination of the HIV-1 viral load and the other for internal control. Each quantification test will be performed in triplicate for each of the samples and for each of the dilutions of the standard line. In each of the tests, negative plasma samples will be used as a target to minimize the impact of possible contaminations in some of the steps of the process. For the quantification (copies/mL) of HIV-1 viral load, only those results within the linear range of the assay ($R>0.95$) will be considered. Initially, the result of the HIV-1 viral load will be validated in those samples where the recovery of internal control is greater than 55%, as described by Palmer et al (20), although this must be previously demonstrated in the process of optimizing our methodology.

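### The ultrasensitive viral load endpoint is pre-specified only as <1 copy/mL at week 24, so a rise within 1–36 copies/mL in a patient already at ≥1 does not register, and no rule secures a quantitative analysis

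*Combined protocol and SAP*

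**What the plan says.** Both endpoint lists define this measure as a week-24 proportion. Section 6.1 has "The proportion of patients with ultrasensitive viral load (<1 copy/mL) after 24 weeks" and section 1.13.2 has "Percentage of patients with virologic response viral load <1 copy/mL after 24 weeks". The next item in section 6.1 is worded differently, as "The change from baseline to 24 weeks in the viral reservoir of peripheral blood mononuclear cells"; the TREC, immune, efavirenz, vitamin D, lipid and renal items are also listed as changes.

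The justification (the text before section 4.1) gives the reason for the assay: it "can discriminate whether this dose-reduction strategy produces any impact on viral replication that cannot be detected by the standard technique".

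Section 9.1 describes a quantitative method: "Each quantification test will be performed in triplicate for each of the samples". It also sets a restriction: "For the quantification (copies/mL) of HIV-1 viral load, only those results within the linear range of the assay" are to be considered. It leaves the linear range, the lower limit of sensitivity and the internal-control recovery threshold (provisionally 55%) to be established in the laboratory.

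Section 6.6 fixes the timing: "All other virologic studies and immunological studies should be determined exclusively at baseline and 24 weeks", with the second sample brought forward if failure is confirmed earlier. The schedules in sections 6.2 and 17 agree.

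Section 11.3 compares proportions by Fisher's exact test. Quantitative data, at both visits and as absolute and relative changes, are compared by the Wilcoxon rank-sum test with Hodges-Lehmann intervals. It does not list the variables that fall under each rule. Section 11.5 rules out imputation and limits the analysis to available data.

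**The concern.** Inclusion criterion 3 in section 7.1 requires a standard viral load below the detection limit. It does not require <1 copy/mL. Some patients may therefore start at 1–36 copies/mL, which is the range the assay was added to observe. If they stay anywhere at or above 1, the named endpoint counts them as not suppressed, whatever happens to their level. Their baseline value, although measured, is not used.

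The pilot is meant to inform a later non-inferiority trial and to show whether dose reduction carries virological risk. A null result on an insensitive endpoint could be taken as reassurance that it does not provide.

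**Working it through.** **Inputs from the documents.** Total sample 60 (section 11.1). Experimental arm: 20% corresponds to n=6 (sections 6.2 and 11.3), so 6/0.20 = 30, which agrees with a 1:1 split of 60; the ratio itself is not stated. Thresholds are 1 and 37 copies/mL. Section 11.1 gives no sample-size calculation, so there is no power figure to reproduce.

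**Step 1: what the dichotomy cannot see.** Take 30 per arm, with the same number k in each arm at 1.5 copies/mL at baseline and the rest <1. Let all k experimental patients rise to 36 and nobody else change. The proportions <1 at week 24 stay equal, (30−k)/30 in both arms, so Fisher p = 1.0 for any k. The rank-sum test on change gives p = 0.08 for k = 3, 0.021 for k = 5 and 0.0006 for k = 10.

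**Step 2: what the dichotomy does see.** It registers moves from <1 to ≥1. Exact Fisher power at 30 v 30 for a fall in the proportion <1:
- 50% to 30%: 0.26
- 50% to 20%: 0.60
- 50% to 10%: 0.91

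**Step 3: power under a general rise.** All distributional inputs here are assumptions. On the log10 scale, baseline = b + e₀ and week 24 = b + e₁ + δ. Here b has mean μ and SD 0.5 between patients, and each e has within-patient SD s. δ = 0.3 (2-fold) in the experimental arm and 0 in the control arm. Values <1 copy/mL are set to 1. The mean is chosen to give the required baseline share at ≥1: μ = Φ⁻¹(share) × √(0.5² + s²).

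Example with s = 0.25 and a share of 70%: √(0.25 + 0.0625) = 0.559 and μ = 0.524 × 0.559 = 0.293. The expected proportion <1 at week 24 is 30% in controls and Φ(−(0.293 + 0.3)/0.559) = Φ(−1.06) ≈ 14% in the experimental arm. Fisher's test sees only that difference.

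Simulated power, 30 per arm, two-sided 5%, 2-fold rise:

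| Share ≥1 at baseline | Fisher, s = 0.25 | Rank-sum on log change, s = 0.25 | Fisher, s = 0.4 | Rank-sum, s = 0.4 |
|---|---|---|---|---|
| 30% | 27% | 61% | 21% | 33% |
| 50% | 27% | 76% | 22% | 42% |
| 70% | 21% | 83% | 16% | 48% |
| 80% | 12% | 87% | 11% | 49% |

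At a 10% share and s = 0.25 the gap is 16% v 33%. At s = 0.5, over shares of 10–80%, it is about 8–20% v 14–35%. Type I error of the rank test stays near 5%. Log change orders patients exactly as the week-24 to baseline ratio does, so this corresponds to the relative change in section 11.3.

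A separate simulation with s = 0.3 and values <1 set to 0.5 gave the same direction. With 20%, 35%, 50% and 70% of patients <1 at baseline, a 2-fold rise gave Fisher 13%, 22%, 25% and 25% against 72%, 69%, 63% and 51% for rank-sum on change.

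**Step 4: does section 11.3 already secure the quantitative analysis?** Its rule could apply, since copies/mL are measured at both visits. But section 9.1 admits only results within the linear range, and section 11.5 analyses only available data. Read together, results <1 could be treated as unavailable and dropped. That would remove the best-suppressed patients, including those who move from <1 to a measurable level.

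**The case against.** A reader might infer that the plan discards the quantitative result altogether, or loses most of the signal. The documents do not support that. The objective in sections 1.10.2 and 5 is ultrasensitive viral load as such, and the quantitative rule in section 11.3 excludes nothing. The dichotomy also captures moves from <1 to ≥1. How much is lost depends on the baseline share at ≥1, which the documents do not give. What remains is that no quantitative ultrasensitive endpoint is named and values <1 have no rule.

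A reader might also infer that this is the only laboratory measure scored as a proportion. It is not: the primary endpoint treats standard viral load the same way. The contrast holds only against the other secondary laboratory markers.

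Two further points stand. With a within-patient SD of 0.4 to 0.5, rank-sum power for a 2-fold rise stays below 50%, so a missed effect would then owe much to 30 per arm as well as to the dichotomy. And precision at 1–36 copies/mL is still to be validated, which is a fair reason to retain a detection-based summary. Neither is a reason to leave the measured change out of the named endpoints.

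**Conclusion.** The concern holds in this limited form. The ultrasensitive endpoint is pre-specified only as a week-24 dichotomy, which fits poorly with the stated purpose of the assay. The generic analysis rule does not reliably repair it. Rank-sum on change had higher power than Fisher's test in every scenario tested with a true rise. For a 2-fold rise and 10–80% of patients at ≥1 at baseline, the figures are about 33–87% v 12–28% at within-patient SD 0.25, and about 14–35% v 8–20% at SD 0.5. The size of the gap rests on assumed log-normal levels, a between-patient SD of 0.5 log10 and unknown assay noise. The direction does not depend on one choice of these inputs. This is a secondary endpoint of a proof-of-concept study, so the primary analysis is untouched, but the change is worth making.

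**What to change.** In sections 1.13.2 and 6.1, name the change from baseline to week 24 in ultrasensitive viral load (copies/mL) as the endpoint, analysed by the rank-sum and Hodges-Lehmann methods already in section 11.3. Add these rules:

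- Results <1 copy/mL, or detectable but below the validated quantification limit, are ranked as tied lowest values, using one common value to compute change. State that they are available data, so that sections 9.1 and 11.5 are not read as removing them.
- Samples that fail internal-control recovery are treated as missing.
- The proportion <1 copy/mL is kept as a companion, cross-tabulated by baseline status (<1 or ≥1).

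The cost is endpoint and analysis wording, plus fixing the quantification limit from the validation that section 9.1 already plans. No visits, samples or assays are added. Two limits remain and should be reported: assay precision at 1–36 copies/mL is not yet established, and 30 per arm gives limited power for small rises under either analysis.
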